10.1.2. Primary Endpoint: Time to Complete Eschar Removal

The main analysis of the primary endpoint time to complete eschar removal will compute missing values as censored at the date of the last non-missing eschar removal assessment (typically last debridement procedure). If no eschar removal assessment after baseline is available, the subject will be censored with time 0.

In addition, three sensitivity analyses will be performed:

- For the first sensitivity analysis, subjects with no available eschar removal assessment
 will be censored with Median Time, estimated using the Kaplan-Meier method based
 on subjects from both treatment groups having a non-missing value on this endpoint
 (including subjects censored at the date of the last non-missing eschar removal
 assessment).
- 2. For the second sensitivity analysis, subjects with no available eschar removal assessment will be censored as follows (a worst case scenario):
 - For NexoBrid with the maximal time obtained for subjects randomized to NexoBrid group (including subjects censored at the date of the last non-missing eschar removal assessment)
 - For SoC with the Median Time, estimated using the Kaplan-Meier method based on subjects from SoC group having a non-missing value on this endpoint (including subjects censored at the date of the last non-missing eschar removal assessment)
- 3. For the third sensitivity analysis, subjects with no available eschar removal assessment will be censored as follows (a best case scenario):
 - For NexoBrid with the Median Time, estimated using the Kaplan-Meier method based on subjects from NexoBrid group having a non-missing value on

this endpoint (including subjects censored at the date of the last non-missing eschar removal assessment)

 For SoC – with the maximal time obtained for subjects randomized to SoC group (including subjects censored at the date of the last non-missing eschar removal assessment)

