9.3. Full analysis Set (Intent-to-Treat population)

The full analysis set (FAS) includes all patients who were randomized into the trial. The analysis is focused on the planned treatment. The analysis of the ITT population (FAS) provides the primary and secondary efficacy and the comparative safety analyses.

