11.1.3. Primary Efficacy Analysis: Time to Complete Eschar Removal

The primary efficacy variable will be analyzed using the FAS. Missing data for the main primary analysis and for the three sensitivity analyses will be handled by the methods described in Section 10.1.2. In addition, the primary analysis will be repeated for the PP collective as sensitivity analysis.

Time until complete eschar removal will be defined as the time until complete eschar removal has been achieved for all TWs. This will be measured as time from the randomization date (days). Kaplan-Meier curves will be presented graphically to display the distribution of time to complete eschar removal under the two treatments. Median time to complete eschar removal

will be estimated for each treatment group with a 95% confidence interval. Furthermore, descriptive statistics for time to complete eschar removal will be presented. The treatment groups will be compared using a Cox regression model. The comparison will be adjusted for clinical center, age, %TBSA, proportion of the FT area of a patient and number of TWs (1,2,3-4, ≥5) by including each of them in the Cox regression model together with the treatment variable (NexoBrid vs. SoC). The treatment groups will be compared by testing the null hypothesis of no difference, comparing the ratio of the estimated treatment coefficient to its standard error to a standard normal distribution.

The Cox Regression analysis outlined above will be performed if the proportional hazards assumption appears to hold. This will be checked by including in the regression model a variable representing the interaction between time since randomization and treatment group. This coefficient will be tested (on actual sample allocation, without the re-randomization test) to be nonzero. Additionally, a log likelihood test comparing the model fit of a model with all time by covariate interactions added with a model without these interactions will be computed. The proportionality assumption will be rejected if one of these tests yields a significant result at the 10% level. In this case, we will use a generalized Wilcoxon-Gehan test. The Wilcoxon-Gehan test will be performed using the Wilcoxon option (also provided by default) in the SAS procedure PROC LIFETEST using the following SAS Code:

```
PROC LIFETEST DATA=burn_data;
TIME time*status(0);
STRATA agegroup ftgroup numtw tbsagroup centergroup / GROUP = treatment_group;
RUN;
```

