Here burn_data is the data set containing all necessary information. The variable time is the time to complete eschar removal, status is a censoring variable (0 for censor and 1 for complete ER event) and agegroup, ftgroup, numtw, tbsagroup, and centergroup are the variables, which the model is adjusted for. Agegroup, ftgroup, tbsagroup and centergroup are the stratification levels defined in Section 11.1.11 and numtw is the number of target wounds $(1, 2, 3-4, \ge 5)$.

Supportive analyses will include adjustment for other baseline variables that are imbalanced, based on the analyses described in Section 11.1.1.

The comparison between treatments will also be conducted on the time to complete eschar removal measured from the date of ICF as an additional analysis.

As an additional analysis, time to complete eschar removal will be analyzed on a target wound level using a method of survival analysis with clustered data that is based on appropriate assumptions. By "clustered data", we refer to the multiple target wounds that can occur in a patient. The proportional hazards assumption will be checked in the same way as in the patient level analysis. I.e. a Cox regression model will be fitted with covariates treatment, center, age, %TBSA, proportion of the FT area of a patient, number of TWs (1,2,3-4, ≥5) and a variable representing the interaction between time since randomization and treatment group. The latter coefficient will be tested to be nonzero. Additionally, a log likelihood test comparing the model fit of a model with all time by covariate interactions added with a model without these interactions will be computed. The proportionality assumption will be rejected if one of these tests yields a significant result at the 10% level. If the proportional hazards assumption is appropriate we will use a marginal Cox regression analysis with a robust sandwich estimator. If not, then we will use a parametric frailty model. Either method can be implemented in SAS (see Gharibvand and Liu, 2009 for details). The marginal Cox regression model is implemented in the PHREG procedure and the robust variance option is implemented by specifying the COVS(AGGREGATE) option. This induces the use of the robust variance method of Binder et. al. [22]. The parametric frailty model will be implemented using the following SAS-code:

```
PROC PHREG DATA=burn_data;

CLASS Subject_id treatment_group centergroup numtw;

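### In the worst-case sensitivity analysis for time to eschar removal, SoC patients with no assessment are handled in a way that favours NexoBrid, so that half is not a worst case

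*SAP*

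**What the plan says.** SAP 9.3 keeps every randomized patient in the primary analysis: "The full analysis set (FAS) includes all patients who were randomized into the trial". Patients who leave after allocation but before any eschar-removal assessment (leavers, below) therefore need a rule.

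SAP 10.1.2 gives the main rule: "If no eschar removal assessment after baseline is available, the subject will be censored with time 0". It then plans three sensitivity analyses for the same patients:

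- **First:** both arms are censored at the pooled Kaplan-Meier median.
- **Second:** "For the second sensitivity analysis, subjects with no available eschar removal assessment will be censored as follows (a worst case scenario". The NexoBrid rule is "For NexoBrid with the maximal time obtained for subjects randomized to NexoBrid group". The SoC rule is "For SoC with the Median Time, estimated using the Kaplan-Meier method based on subjects from SoC group having a non-missing value".
- **Third (best case):** the arms are swapped, with NexoBrid leavers censored at the NexoBrid median and SoC leavers at the SoC maximum.

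SAP 11.1.3 fixes the coding, "status is a censoring variable (0 for censor and 1 for complete ER event", and the test: "The treatment groups will be compared using a Cox regression model". A generalized Wilcoxon-Gehan test replaces Cox if proportional hazards is rejected.

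**The concern.** The event is the good outcome. A patient censored at time t is treated as having gone until t without eschar removal. Moving an SoC leaver from time 0 to the SoC median turns a patient who contributed nothing into one who stayed undebrided for that long. That makes SoC look slower. A scenario meant to be pessimistic for NexoBrid should make SoC leavers look fast.

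None of the three scenarios counts a leaver as an event. If leavers were all in the SoC arm, all three would move the estimate towards NexoBrid, and the one labelled worst case could be reported as evidence of robustness. The study is open, so withdrawal that differs by arm after allocation is the pattern such a check should test. For other endpoints the SAP does change the outcome itself: missing surgical excision and autograft incidence are set to failure in one analysis and success in another (10.1.3.1, 10.1.3.4), and missing MVSS is set to 9 and then to 0 (10.1.4.2).

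**Working it through.** **Inputs from the documents.** Time-0, median and maximum censoring rules (SAP 10.1.2); event coding and tests (11.1.3); 1:1 allocation (11.1.11); 145 patients enrolled (13.3); target log hazard ratio -1.25 for SoC versus NexoBrid, hazard ratio 0.29 (9.1.1). Inverted, 1/0.29 = 3.45 for NexoBrid:SoC, so values above 1 favour NexoBrid.

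**Assumed, not in the documents.** 72 versus 73 patients, exponential times, SoC median 6 days, and the number of leavers.

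**1. The plan's own figure.** D = 4(1.96 + 1.28)²/1.25² = 41.99/1.5625 = 26.9 events; n = 2 × 26.9/(0.59 + 0.70) = 41.7, so 42. SAP 9.1.1 reproduces.

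**2. Direction, without simulation.** The Cox score for the NexoBrid log hazard ratio b is

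U(b) = Σ [ s − d·nN·e^b / (nN·e^b + nS) ],

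summed over event times, where s is NexoBrid events, d is all events, and nN and nS are the numbers at risk. An SoC leaver censored at the SoC median adds 1 to nS at each event time up to that median and leaves s and d unchanged. The subtracted term shrinks, U rises at every b, and the estimate moves towards NexoBrid. A NexoBrid leaver censored at the NexoBrid maximum adds to nN with no event and moves it the other way.

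**3. Leavers in the SoC arm only (unadjusted Cox).** The 0/8 rows come from a separate run of the same design; the others use 400 simulated trials each.

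| Leavers NexoBrid/SoC | True HR | Main | Planned worst case | Shift |
|---|---|---|---|---|
| 0/1 | 1.5 | 1.508 | 1.525 | 1.1% |
| 0/4 | 1.5 | 1.501 | 1.571 | 4.7% |
| 0/7 | 1.5 | 1.505 | 1.634 | 8.6% |
| 0/7 | 3.45 | 3.490 | 3.897 | 11.7% |
| 0/8 | 1.4 | 1.42 | 1.56 | 9.9% |
| 0/8 | 3.45 | 3.51 | 3.98 | 13.4% |

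The shift is the ratio minus 1 (for example 1.56/1.42 = 1.099). Divided by the number of leavers, it is 1.1 to 1.7% each. The planned worst case exceeded the main estimate in 100% of runs, for Cox and, where it was run, for Gehan. At 0/7 and true HR 1.5 the share significant for NexoBrid rose from 64% to 80%.

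**4. Leavers in both arms (Cox).**

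| Leavers NexoBrid/SoC | True HR | Main | Planned worst case |
|---|---|---|---|
| 1/3 | 1.4 | about 1.41 | 1.35 |
| 2/6 | 1.4 | about 1.41 | 1.33 |
| 4/4 | 1.4 | about 1.41 | 1.17 |
| 1/7 | 1.5 | 1.499 | 1.513 |
| 2/7 | 1.5 | 1.512 | 1.436 |

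Once NexoBrid has a meaningful share of leavers, its maximum-time rule dominates. It does so more slowly under an unstratified Gehan test: at 2/7 and true HR 1.5 the mean z still rose, from 1.99 to 2.23, while at 4/4 it fell from 1.98 to 1.66.

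Even below the main result, the scenario is less pessimistic than its label. At true HR 1.5, counting SoC leavers as events at the SoC median, with the NexoBrid rule unchanged, gives 1.17 rather than 1.24 at 4/4, and 1.02 rather than 1.13 at 7/7.

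**5. Mirror fault in the best case.** With 8 NexoBrid-only leavers at true HR 3.45, the best case gives 3.31 against a main estimate of 3.51.

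**6. Effect of changing the status.** With 0/8 leavers, SoC leavers counted as events at the NexoBrid median (300 trials):

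| True HR | Main | Planned worst case | SoC leavers as events |
|---|---|---|---|
| 1.0 | 0.98 | 1.07 | 0.95 |
| 1.4 | 1.42 | 1.55 | 1.33 |
| 3.45 | 3.49 | 3.95 | 2.97 |

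The event time matters. At 0/7 and true HR 3.45, an event at the SoC median gives 3.55, still above the main 3.49, so an earlier time is needed.

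**The case against.** The strongest reply is that the scenario is a package and its NexoBrid half is severe. At 1/3, 2/6 and 4/4 the planned worst case falls below the main Cox estimate. At true HR 1.4, main, worst and best average 1.41, 1.36 and 1.56 for 1/3, and 1.39, 1.16 and 1.56 for 4/4, so the two scenarios do bracket the main result. This stands. A reader might infer that the worst case always flatters NexoBrid, or that the scenarios never bracket the main result. The rules in 10.1.2 do not support that; it needs leavers only or almost only in one arm, though under Gehan the imbalance need not be so extreme.

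The affected group may also be very small. For surgical excision, whose window likewise ends at complete eschar removal, SAP 10.1.3.1 expects little or no missing data. One SoC leaver moves the estimate by 1 to 2%. Nothing in the documents shows that families withdrew on learning of SoC allocation, and 8 SoC-only leavers is an illustration. This also stands, and it limits the size of the point, not its direction.

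Finally, the simulations omit covariates, strata and, for most runs, ordinary censoring, although SAP 9.1.1 cites event proportions of 0.59 and 0.70. The sizes are therefore indicative. The direction rests on the score argument, which does not use those assumptions.

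**Conclusion.** The point holds in a limited form. Censoring SoC leavers at the SoC median favours NexoBrid relative to the main analysis, so the SoC half of the planned worst case is wrong as written. With leavers only or almost only in the SoC arm, the labelled worst case exceeds the main estimate, by about 1 to 2% per leaver. With a meaningful share on NexoBrid it falls below the main Cox estimate but is milder than its label implies. The best case has the mirror fault for NexoBrid-only leavers. These sizes rest on exponential times and assumed leaver counts.

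A reader might infer that the primary result itself is biased. The documents do not support this: the re-randomization p-value (SAP 11.1.2) and the testing hierarchy (11.1.9) use the main analysis, which these scenarios do not touch. If the true effect is near the target of 3.45, the conclusion is unlikely to change. What is at stake is whether the sensitivity analysis can be cited as a stress test for SoC withdrawals. As planned, it cannot.

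**What to change.** In SAP 10.1.2:

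- **Worst case:** keep NexoBrid leavers censored at the NexoBrid maximum; count SoC leavers as events (status = 1) at an early time such as the NexoBrid Kaplan-Meier median.
- **Best case:** count NexoBrid leavers as events at the NexoBrid median; keep SoC leavers censored at the SoC maximum.
- Report the number of leavers per arm beside both results.
- Describe these as pessimistic and optimistic scenarios, not strict bounds, because an event time earlier than the NexoBrid median would be more extreme still.

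There is no need to move NexoBrid censoring to the longest time in the whole trial. With 8 NexoBrid-only leavers at true HR 3.45 that would give 1.44 rather than 2.08 under the present rule, and the present rule already counts against NexoBrid.

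The cost is a few lines of SAP text and a changed status flag. The downside for the sponsor is a worst-case result less favourable to NexoBrid whenever there are SoC leavers.

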10.1.3. Secondary Endpoints

10.1.3.1. Incidence of Surgical Excision

Little or no missing data are expected for the secondary endpoint incidence of surgical excision. The main analysis will include all randomized patients, with those having a missing value assumed to have "failed", i.e. to have received surgery. Two sensitivity analyses will be performed. First, in each treatment group, only patients with documented surgical excision will be counted and this number divided by the total number of randomized subjects with non-missing endpoint. A second analysis will include all randomized patients and count all patients with missing data (for this endpoint) as "success" (i.e. no surgical excision performed).

Note: The main analysis specified in the protocol was the complete case analysis. However, in previous discussions concerning the study MW2010-03-02, FDA suggested to use all subjects for the main analysis of this endpoint. Therefore, in the previous study, the main analysis included all subjects with those having a missing value assumed to have "failed", i.e. to have received surgery. This approach was also adopted here.

10.1.3.2. Blood Loss

As defined in Section 10.3.3.2.1, the measure of blood loss per patient will be computed using two different methods:

- Method 1: treating the whole eschar removal process as one continuous procedure
- Method 2: summing the blood loss computed per procedure over all procedures carried out to remove eschar

Missing blood loss values will be imputed separately for each method. The procedures can be described as follows:

1. Test for normality:

- For Method 1: The measure of blood loss defined in Section 10.3.3.2.1 will be computed for each patient.
- For Method 2: The measure of blood loss defined in Section 7.2.2.210.3.3.2.1
 will be computed for each procedure and aggregated to patient level.

An ANOVA model (on a patient level) incorporating the stratification factors treatment center, %TBSA, proportion of the FT area and age will be used to detect differences between both treatment groups. The normality of the data will be tested on residuals of this model using the Shapiro-Wilk test. If the normal distribution hypothesis is not rejected at the 5% significance level, then the ANOVA model will constitute the main analysis model. In case the normal distribution hypothesis is rejected at the 5% significance level, then a stratified Wilcoxon test, using the same stratification variables as outlined for the ANOVA, will be used.

2. Imputation:

If the normality condition is satisfied, the following will be performed:

- For Method 1: Fit a linear regression model with target variable blood loss on a
 patient level (as computed in Section 10.3.3.2.1) and independent variables
 age, wound area, depth of wound (categorized as all DPT / mixed / all FT) and
 course of debridement procedure (as defined in Section 10.3.3.2.5) to the
 subset containing patients with complete data in those variables for both
 treatment groups separately.
- For Method 2: Fit a linear regression model with target variable blood loss on a procedure level (as computed in Section 10.3.3.2) and independent variables age, size of wounds treated in this procedure (wound area), proportion of area SPT of wounds treated in this procedure (as defined in Section 10.3.3.2.2), proportion of area DPT of wounds treated in this procedure (as defined in Section 10.3.3.2.3), proportion of area FT of wounds treated in this procedure (as defined in Section 10.3.3.2.4) and type of procedure (surgical/non-surgical) to the subset containing patients with complete data in those variables for both treatment groups separately. This model will treat all the procedures as independent.

Impute the missing entries of the incomplete data sets m = 25 times as follows. Draw a set of regression coefficients from their sampling distribution obtained from fitting the respective linear models outlined above. Sample a variance as the quotient between the residual variance from the linear model fitted to the data and a random variable which is chi-square distributed with corresponding degrees of freedom (a different distribution for the regression coefficients and variance will be obtained in the different treatment groups). With these sampled coefficients calculate the predicted blood loss values for the missing blood loss values using the covariate information. To these predicted blood loss values add the realizations of a normally distributed random variable with zero mean and standard deviation equal to the sampled standard deviation. The imputation outlined above will be performed using PROC MI in SAS. If the normality condition is not satisfied, then the multiple imputation method known as predictive mean matching will be used. Random draws from the five nearest neighbors for each missing value, and m=25 multiply imputed datasets will be used. The predictive mean matching method is implemented in the SAS procedure PROC MI.

- For Method 1: The random seed will be 12467.
- For Method 2: The random seed will be 1732. On the imputed datasets the blood loss on a patient level will be calculated.
- 3. Analysis: Analyze each of the m complete datasets with an ANOVA or the stratified Wilcoxon test according to the test result in step 1 using the re-randomization test outlined in Section 11.1.2. An estimated treatment difference, δ (NexoBrid versus SoC), from the analysis model and a two-sided p-value, p, from the permutation test (as described in Section 11.1.2) will be obtained for each imputed dataset. In case the analysis is performed with the stratified Wilcoxon test, Hodges-Lehmann (HL) estimate for treatment difference will be used (options ALIGN=STRATA WILCOXON HL in SAS NPAR1WAY procedure).
- 4. Pooling: Integrate the m analysis results into a final result, as follows. A "working standard error", s, of the estimated treatment difference for each imputed dataset will be obtained by $s = \delta/\Phi^{-1}(1-p/2)$ if $\delta>0$, or $s = \delta/\Phi^{-1}(p/2)$ if $\delta<0$, where Φ^{-1} is the inverse of the standard normal cumulative distribution function. Then Rubin's rules will be used to combine the set of values of δ and s (using PROC MIANALYZE in SAS) to give an overall estimate of δ and its standard error.

- 5. The p-values (p_{1, ...,} p_m) will be combined using the Licht-Rubin formula (as described in Section 4.1 of [16]), as follows:
 - 1) Compute $z_i = \Phi^{-1}(1-p_i)$ for each i
 - 2) Compute the mean: $\bar{z} = \frac{1}{m} \sum_{i=1}^{m} z_i$
 - 3) Compute the between variance: B = $\frac{1}{m-1}\sum_{i=1}(z_i-\bar{z})^2$
 - 4) Compute the total variance: $T = 1 + (1 + m^{-1})B$
 - 5) Compute the relative variance increase due to non-response: $r = (1 + m^{-1})B$
 - 6) Compute the degrees of freedom: $v = (m-1)(1+r^{-1})^2$
 - 7) The final p-value is then: $\Pr[t_{\nu} > \overline{z}/\sqrt{T}]$ where t_{ν} is the t-distribution with ν degrees of freedom.

Analyses with both blood loss values will be conducted. However, the analysis with less missing values will be regarded as more reliable and is therefore considered the main analysis. The other analysis is considered supportive.

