10.1.3.3. Area of Autograft in DPT Wounds

Very few cases of missing data are expected to be observed in the secondary endpoint of percentage of wound area autografted in DPT wounds. Any missing data for percent area autografted will be imputed using the multiple imputation method. The procedure can be described as follows:

- 1. Imputation: The imputation model will be built on a subject level by multiple linear regression of known percent area autografted on center, total area of TWs, %TBSA, number of TWs (1,2,3-4,≥5), age and sex, and will be carried out separately within each treatment group. Once the model is estimated, the imputed values will be obtained from the value predicted by the model plus a residual term that will be drawn at random from the estimated residuals. The random seed will be 141421. Twenty five (m=25) imputed datasets will be created.
- Analysis: Each of the m complete datasets will be analyzed using a linear regression model. The explanatory variables in the model will include treatment, center, age, %TBSA, proportion of the FT area of a patient and number of TWs (1,2,3-4,≥5). An

estimated treatment difference, δ (NexoBrid versus SoC), from the analysis model and a two-sided p-value, p, from the permutation test (as described in Section 11.1.2) will be obtained for each imputed dataset.

3. Pooling: The m analysis results will be integrated into a final result – an overall estimate of δ , its standard error, and the final p-value, as described in Section 10.1.3.2 (items 4 and 5).

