10.3.3.2. Blood Loss

10.3.3.2.1. Blood Loss Calculation

Blood loss will be calculated using the following formula [15], [48]:

$$Blood\ Loss\ (mL) = \frac{RBCV_{before} + (Transfusion\ RBCV) - RBCV_{after}}{Hct_{after} [\%] * 0.01}$$

RBCV (mL) = Red Blood Cell Volume (mL) = Body Weight (kg) * 80 (mL/kg) * (Hematocrit [%] * 0.01)

Transfusion RBCV (mL) = [Total Volume (mL) of Whole Blood Transfused * 0.3] + [Total Volume (mL) of Packed Red Blood Cells Transfused * 0.8]

The blood loss will be computed over the whole eschar removal period, using the formula above, i.e. the eschar removal process will be considered as one continuous procedure. Therefore, only the Hematocrit value before the first eschar removal procedure and after the last procedure will be used and all blood transfusions performed between these measurements will be included.

Additionally, the blood loss will be summed over all procedures carried out to remove eschar, with the hematocrit measured immediately before each procedure and 4 hours after its completion. The amount of blood transfused will be summed over all transfusions carried out during the debridement procedure and up to 24 hours from the end time of the debridement procedure.

Analyses with both blood loss values will be conducted. However, some missing values are expected. The analysis with less missing values will be regarded as more reliable and is therefore considered the main analysis. The other analysis is considered supportive.

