11.1.11. Stratification

The following factors are used to stratify the study design:

A. Age group:

A1: 0 to 23 month

A2: 24 months to 3 years

A3: 4 to 11 years

A4: 12 to 18 years

B. Overall total area of burns measured by % of TBSA

B1: (1% to 15%), inclusive

B2: (> 15% to \leq 30%)

C. The proportion of the FT area out of the total burned area of a patient

C1: < 20% of the burned area defined as FT

C2: ≥ 20% of the burned area defined as FT

D. Clinical center, so as to address possible differences in SoC procedures between sites (if any), to allow comparison of the results within center and to reduce the likelihood of a center including patients in only one arm of the study.

 $D_1, D_2,...,D_m$ (m being the number of participating clinical centers).

Using this stratification, patients will be randomized in a 1:1 ratio (NexoBrid: SoC).

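### The blood-loss imputation models leave out center and transfused red-cell volume, so the arm difference can be biased if missing values depend on either

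*SAP*

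**What the plan says.** Blood loss is computed from a formula (SAP 10.3.3.2.1) using body weight, hematocrit before and after, and transfused red-cell volume. For the whole-period version (Method 1), "all blood transfusions performed between these measurements will be included". Transfused volumes are collected on the eCRF (10.3.4.4).

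When a value is missing, 10.1.3.2 imputes the blood loss itself, separately by arm, with 25 imputations:

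- Method 1 predictors: "age, wound area, depth of wound (categorized as all DPT / mixed / all FT) and" "course of debridement procedure (as defined in Section 10.3.3.2.5) to the" complete cases.
- Method 2 predictors, per procedure: "age, size of wounds treated in this procedure (wound area), proportion of area SPT of wounds treated in this procedure", then the DPT and FT proportions and whether the procedure was surgical.
- In the normal-theory branch: "With these sampled coefficients calculate the predicted blood loss values for the missing blood loss values using the covariate information". If normality is rejected, predictive mean matching is used instead.

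The analysis model in the same section is "An ANOVA model (on a patient level) incorporating the stratification factors treatment center, %TBSA, proportion of the FT area and age"; 11.1.8 groups center into four regions. The autograft-area imputation (10.1.3.3) regresses "known percent area autografted on center, total area of TWs, %TBSA, number of TWs" and further covariates. The MVSS imputation (10.1.4.2) uses all stratification variables, and these include center.

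**The concern.** An imputation model should contain at least the variables of the analysis model. Otherwise the imputed values carry no site effect and are pulled toward the pooled mean of their arm. In the blood-loss analysis model, %TBSA and FT proportion have rough counterparts in the imputation lists (wound area, depth), and age is in both. Center has no counterpart. The SAP stratifies by center "so as to address possible differences in SoC procedures between sites", while allowing that there may be none, and it gives no reason for leaving center out here alone.

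Transfused volume is a different case: it is part of the outcome. A transfused child with a missing sample can be given an imputed loss that takes no account of the recorded transfusion.

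At stake are the reported treatment difference and its standard error for the third endpoint in the hierarchy of 11.1.9, which also gates both autograft endpoints.

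**Working it through.** **1. How much imputation is planned.** Appendix 13.3 inflates the blood-loss sample size for 30% missing values. For MW2004-11-02, 346/0.7 = 494.3 (stated: 494). For MW2010-03-02, 56/0.7 = 80 (stated: 80). The planning figures reproduce, so imputation is not a marginal matter for this endpoint.

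**2. The lists side by side.**

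| Variable | Blood-loss analysis | Blood-loss imputation (both methods) | Autograft-area imputation | MVSS imputation |
|---|---|---|---|---|
| Center | yes | no | yes | yes |
| Transfused RBC volume | part of the outcome | no | not relevant | not relevant |

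**3. What the transfusion term can weigh.** Rearranging the SAP formula:

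loss = 80 × weight × (Hct before/Hct after − 1) + transfused RBCV/Hct after.

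Take an assumed child of 20 kg given 300 mL packed cells, with a final hematocrit of 30% and the earlier sample missing. The second term is known: 300 × 0.8/0.30 = 800 mL. The unknown first term is 1600 × (0.32/0.30 − 1) = 107 mL to 1600 × (0.38/0.30 − 1) = 427 mL for an earlier hematocrit of 32–38%. The planned model imputes the sum without using the 800 mL. This describes one child; it is not an effect on the arm difference.

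**4. Center, by algebra.** Assume two equal halves of sites with mean losses a and b, and missing rates of 10% and 50%. The observed mean is (0.45a + 0.25b)/0.70 = 0.643a + 0.357b. Filling missing values with that mean shifts the arm mean by 0.05 × (−0.357)(a − b) + 0.25 × 0.643(a − b) = 0.143(a − b). With assumed site contrasts of 400 mL in SoC and 40 mL in NexoBrid, the arm difference moves by 0.143 × 360 = 51 mL. That is 51/722 = 7% to 51/465 = 11% of the planning differences (13.3 and 9.1.3). The direction depends on which sites lose samples. The figure also assumes that the listed covariates explain none of the site contrast.

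**5. Simulation under assumed inputs.** Settings: 145 children, about 30% missing with one hematocrit lost, 500–600 runs per scenario, 5 imputations, mean difference between arms. The complete-data difference was about 80 mL and the Monte Carlo error about 1 percentage point. Positive bias means toward no difference.

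| What drives missingness | Planned, linear | Planned, matching | Impute hematocrit, then formula | RMSE (mL): planned / hematocrit |
|---|---|---|---|---|
| Nothing | −1.2 to −1.1% | −0.8 to −0.4% | −2.4 to −0.3% | 16.5–18.6 / 17.1–17.4 |
| Low starting hematocrit | 0.3% | 0.0% | −1.1% | 16.7–17.5 / 21.1 |
| Transfused more often missing, both arms | 1.7 to 7.7% | 3.5 to 9.6% | 0.6 to 2.3% | 18.0–21.2 / 18.7–48.5 |
| Transfused less often missing, both arms | −2.8 to 0.4% | −3.1 to −2.0% | −1.6 to 2.1% | 16.5–18.9 / 17.2–18.7 |
| One region | 2.7 to 6.1% | 3.1 to 6.7% | −1.1 to 0.4% | 17.7–19.7 / 20.8–26.0 |
| Transfused more often missing, SoC only | 14.0 to 16.9% | 17.3 to 19.2% | −17.2 to −14.3% | 22.7–24.6 / 33.0–46.3 |

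**6. The smaller change.** In a further simulation with assumed inputs, the planned covariates gave about 3–4% bias toward no difference when missingness followed transfusion and about 8% when it followed region. Adding grouped center and transfused volume reduced this to about 2% or less. With values missing completely at random there was almost no bias.

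**The case against.** The case on the other side is substantial.

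- **No stated mechanism.** The documents do not say which samples go missing or why. Every size above rests on an assumed pattern. This stands, and it makes the sizes illustrative.
- **Existing covariates carry some of the information.** Fitting by arm with course of debridement or procedure type captures part of both transfusion and site practice. It does not capture the volume, or site differences within a course category.
- **Partial protection elsewhere.** Section 10.3.4.4 reuses neighbouring samples for planned missing values, Method 2 keeps procedures with observed loss, and both methods are run. Unplanned gaps remain.
- **Estimand.** If normality is rejected, the estimate is Hodges-Lehmann, which is less sensitive to a few large values. A rough check with 60% against 24% missing by transfusion status gave 25–30% bias on means and 11–19% on the Hodges-Lehmann scale. The scale and the assumed mechanism both matter.
- **Direction.** Most of the biases run against NexoBrid, and no inflated false-positive risk is shown. A biased estimate is still worth avoiding.

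A reader might go further and infer that the plan must impute the hematocrit instead of blood loss, because the other sample is usually on record. The documents do not say that it is; 10.3.4.4 excludes samples outside the time window, so both may be unusable. Nor was that method reliably better: it was 14–17% biased the other way when missingness followed transfusion in SoC only, and its error was often larger.

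**Conclusion.** The concern holds as a conditional one. Both blood-loss imputation models omit center, which the analysis model and the SAP's other regression imputations include, and transfused RBC volume, which is a recorded component of the outcome. If missing values depend on either, the arm difference can be biased, by roughly 2–10% toward no difference in most assumed scenarios. It was 14–19% when transfusion raised missingness in SoC only, and up to about 3% in the opposite direction when transfused children lost fewer samples. If missingness depends on neither, there is little or no bias.

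A reader might also infer that the planned result is known to be biased, or that the change would buy precision or power. Neither is supported: the pattern of missing samples is not given, and the error was often unchanged or larger under the alternative method. The planning differences come from one study with adults and children and one in adults (9.1, 13.3), whereas 75 of the 145 children enrolled are aged 3 or under (45 + 30). Percentages of those differences may therefore not carry over.

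**What to change.** In 10.1.3.2, add two predictors to both listed imputation models, keeping the fit by arm and m = 25:

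1. the grouped center of 11.1.8;
2. transfused RBC volume as defined in 10.3.3.2.1 (for Method 2, the volume attributed to the procedure), or transfused yes/no if few children in an arm were transfused.

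As a sensitivity analysis only, impute the missing hematocrit where the other sample and body weight are available, then apply the 10.3.3.2.1 formula in each dataset. Report missing blood-loss values by arm, region and transfusion status, so that readers can see whether the condition for bias is met.

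The cost is SAP wording and a few programming lines, since the variables are already collected. The statistical price is about four parameters per arm (three region indicators and one transfusion term). At 30% missing, they are fitted to about 145/2 × 0.7 = 51 complete patients per arm. If 7–17% of SoC children were transfused (an assumption), that is only about 5–12 children before any loss of samples. The transfusion coefficient could then be unstable, and the variance may rise slightly.
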